### **Secondary outcomes:**

#### **1. Outcomes of the Wasp task**

The number of wasps hit (#wasps) and the anterior-posterior weight-shifting error (error from the ideal trajectory) will be used within the Wasp Game. The trajectory error will be determined similar to the primary behavioral outcome measure. #wasps hit and trajectory error will be compared between the three test moments (pre, post, retention) and between the two groups (training, control).

#### **2. Functional limits of stability.**

These will be determined in eight different directions (anterior, anterior-right, right, posterior-right, posterior, posterior-left, left, anterior-right) and compared between the three test moments (pre, post, retention) and between the two groups (training, control).

#### **3. fNIRS-outcomes**

For the neural outcome, cortical oxygenated hemoglobin (HbO2) will be measured with functional Near-Infrared Spectroscopy (fNIRS) in the prefrontal cortex (PFC), frontal eye fields (FEF), premotor cortex (PMC), supplementary motor area (SMA) and the somatosensory cortex (SSC) . HbO2 levels will be determined and compared between the three test moments (pre, post, retention) and between the two groups (training, control) during the Wasp Game ST and Wasp Game DT.

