Recent systematic reviews showed that postural control in older adults can be improved with training¹⁵. However, little is known about the ability and maintenance of re-learning to weight-shift, let alone about its underlying mechanism. Therefore, the primary aim of this project will address this lacuna by studying the effects of training in weight-shifting performance in older adults and its underlying neural imprint. As our previous study (unpublished) showed that adding an extra cognitive task in a so-called dual-task (DT) negatively affects weight-shifting performance, a secondary aim will be to test whether weight-shift training will enhance performance during such DT conditions. The results of this study might form a basis for future technology-based rehabilitation programs.

4 Study objectives

The effects of postural learning on cortical activity have not been identified yet in older adults. During non-postural tasks, older adults needed greater activity and recruited more brain areas during automatization compared to young adults. This is suggested to be the primary reason for impaired motor automaticity with age¹⁶. We will use fNIRS to examine postural learning in the upright position for the first time in older adults. More specifically, we will investigate:

1. Changes in brain activity in frontal, (pre-)motor, and parietal regions associated with the acquisition and consolidation of weight shifting in older adults. In addition, as moving the Centre of Mass (CoM) deliberately also loads sensorimotor function, we will include the parietal cortex as region of interest.
2. Changes in brain activity in frontal, (pre-)motor, and parietal regions associated with the acquisition and consolidation of weight shifting compared to no training (control group).
3. Changes in brain activity in frontal, (pre-)motor, and parietal regions associated with the transfer of single-task acquisition and consolidation of weight shifting to dual-task weight shifting performance.

5 Methodology of the research

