5.4 Equipment

Postural outcomes will be measured on the Computer Assisted Rehab Environment (CAREN) (Motek Medical BV, Amsterdam) with integrated force plates. Spherical reflective markers placed bilaterally on anatomical landmarks will allow 3D-kinematic analysis with 7 MX-T20 optoelectronic cameras (Vicon, Oxford Metrics, UK), which will be done both online with D-Flow software (Motek Medical BV, Amsterdam) as offline. Changes in the brain hemoglobin concentrations will be registered with a wireless 16-16 fNIRS system (NirXsports 2), which has the required resolution and coverage to meet the study objectives. Sixteen optodes per hemisphere will be placed over the prefrontal, posterior parietal and premotor, SMA and M1 regions with an inter-optode distance of 35 mm, placed on an EEG-cap using the 10-20/10-10/10-5 EEG system.

6 Statistics, data handling and data management

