6.2 Data analysis and statistics

Calculation of the CoM data will be processed using Nexus 2.4 and customized Matlab scripts. Body movement during postural control, comprising CoM displacement, deviation of trajectory and speed will be calculated. To account for motion artefacts during fNIRS measurements, we will perform visual checks and signal processing techniques, including filtering and noise removal. A linear mixed model will analyze learning effects with training group as between-subject and pre-post-retention as within subject factor.

7 Safety

There are no permanent risks involved for the subjects participating in this study. All experiments are painless and harmless for participants. A safe and existing test infrastructure will be used and experienced researchers will conduct the experiments. Participants will be informed about the procedure and possible risks of the tests before the start of the experiment. Some of the participants may feel some fatigue during the weight shifting trials. To prevent excessive fatigue, participants will be encouraged to take breaks as needed in-between all trials. The fNIRS head cap will be cleaned/washed after each participant to ensure appropriate adherence to infection control policies. Based on a recent PhD thesis on the development and validity of the WASP task [de Vries, A (PhD thesis, March 2018)] we do not anticipate that any risks will be involved in the use of this WASP task.

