### **Brief summary:**

Older people show deficits in dynamic weight-shifting, as we found that more time is needed to perform weight-shifts and the movements become less fluent and accurate in older versus younger adults. Deficits with weight-shifting in the mediolateral (left-right) direction has been linked to balance and falls in ageing. Balance control can be improved with training. Virtual reality (VR) based training programs for improving balance are gaining ground, as it can provide both fun and challenging balance tasks, enhancing motivation. We demonstrated earlier that older adults show an overloaded neural activation pattern compared to young adults when performing the same VR-based mediolateral weight-shifting task (wasp game). What is yet unclear, is whether improved balance capacity can be gained with training and whether such an intervention impacts the underlying neural mechanisms. Using a combination of behavioral assessments and functional Near-Infrared Spectroscopy (fNIRS), the primary aim of this study is to investigate the effects of a VR-based weight-shift training and its underlying neural imprint in older adults. Furthermore, as our previous study also showed that adding an extra cognitive task in a so-called dual-task (DT) negatively affects weight-shifting performance, a secondary aim will be to test whether weight-shift training will enhance performance during such DT conditions. The results of this study may contribute to the future design of technology-based rehabilitation programs.

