## 2. fNIRS-outcomes

Cortical deoxygenated hemoglobin (HHb) will be measured with functional Near-Infrared Spectroscopy (fNIRS) in the same regions as HbO2. HHb levels will be determined and compare between the three test moments (pre, post, retention) and between the two groups (training, control) during the Wasp Game ST and Wasp Game DT.

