### **Main analysis:**

Primary, secondary and tertiary outcomes will be compared between training and control group and pre, post and retention test using linear mixed models. We will determine the best model based on standard fitting criteria. . We will consider cognitive and balance skills as possible covariates, depending on between group differences and determined by a blind review of the data. Post-hoc testing will be corrected for multiple testing by Bonferroni corrections.

Depending on data normality, Pearson and/or Spearman correlation analysis will be performed between neural and behavioral outcomes within groups and test moments. Bonferroni corrections for multiple testing will be applied when necessary.

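### Do the differing fNIRS region lists, and the lack of a stated test family across regions and tasks, require a change to the plan?

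*SAP*

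**What the plan says.** Protocol section 4 sets its objectives in broad terms. Objective 2, for example, reads "Changes in brain activity in frontal, (pre-)motor, and parietal regions associated with the acquisition and consolidation of weight shifting compared to no training". Objective 1 adds that moving the centre of mass "also loads sensorimotor function, we will include the parietal cortex as region of interest". Protocol 5.4 then describes the hardware: "Sixteen optodes per hemisphere will be placed over the prefrontal, posterior parietal and premotor, SMA and M1 regions", with 35 mm spacing on a standard EEG cap layout.

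The SAP lists the analysed regions. Oxygenated haemoglobin (HbO2), a secondary outcome, is measured "in the prefrontal cortex (PFC), frontal eye fields (FEF), premotor cortex (PMC), supplementary motor area (SMA) and the somatosensory cortex (SSC"). For deoxygenated haemoglobin (HHb), a tertiary outcome, the SAP says "Cortical deoxygenated hemoglobin (HHb) will be measured with functional Near-Infrared Spectroscopy (fNIRS) in the same regions as" HbO2. Both are compared over three test moments and two groups, in the single task (ST) and the dual task (DT).

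On the model, Protocol 6.2 says "A linear mixed model will analyze learning effects with training group as between-subject and pre-post-retention as within subject factor". The SAP's Main analysis says "Primary, secondary and tertiary outcomes will be compared between training and control group and pre, post and retention test using linear mixed models". It adds that the best model will be picked by the usual fit criteria, that post-hoc tests are Bonferroni-corrected, and that the same correction applies to the correlations where needed. It does not say how region and task enter the model, or which group-by-time tests form a family.

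**The concern.** Two things look wrong.

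First, the cap and the analysis do not name the same places. Frontal eye fields (FEF) and somatosensory cortex (SSC) have an outcome but no named optodes. Primary motor cortex (M1) and posterior parietal cortex have optodes but no outcome. Without a channel map, a reader cannot tell whether regions were relabelled, swapped or dropped after the protocol was written.

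Second, five regions and two tasks leave room for ten group-by-time tests on HbO2 alone, and ten more on HHb. The Bonferroni rule covers the follow-up comparisons but does not say what protects the tests that come before them. One positive region could then be presented as a training effect on the brain. All three protocol objectives concern brain activity, and the SAP's Brief summary says "the primary aim of this study is to investigate the effects of a VR-based weight-shift training and its underlying neural imprint in older adults", so such a claim would be prominent.

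**Working it through.** The plan states no number of fNIRS tests, no family-wise error rate and no fNIRS power, so there is no planned figure to reproduce. The sample size of 40 in Protocol 5.1 rests on weight-shifting speed and does not bear on this point.

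**Step 1: the labels side by side**

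| Protocol 5.4 (optodes) | SAP (outcomes) | Match |
|---|---|---|
| Prefrontal | PFC | yes |
| Premotor | PMC | yes |
| SMA | SMA | yes |
| M1 | none | no |
| Posterior parietal | none | no |
| none | FEF | no |
| none | SSC | no |

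Three of five match. This counts names, not channels. FEF is a frontal label and SSC a parietal one, so both fall inside the broad groups of Protocol section 4. SSC also fits the sensorimotor reason given there for including parietal cortex. The mismatch is therefore with the wording of the equipment section and not clearly with the objectives.

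**Step 2: error rate if every region and task has its own model**

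Inputs: 5 regions, 2 tasks and alpha 0.05 (the level used in Protocol 5.1). Number of tests: 5 × 2 = 10.

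Under independence, the chance of at least one false positive is 1 − 0.95^10 = 0.401.

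The tests share participants, so they are probably correlated. The documents give no correlation, so a range is assumed. Simulation used 20 per group, three test moments, a group-by-time F test on 2 and 76 degrees of freedom, and 20,000 runs:

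| Assumed correlation | At least one false positive in 10 |
|---|---|
| 0 | 0.400 |
| 0.3 | 0.359 |
| 0.5 | 0.300 |
| 0.7 | 0.225 |

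**Step 3: error rate if region and task are factors in one model**

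Four terms contain group-by-time: alone, with region, with task, and with both. Reading all four at 5% gives 1 − 0.95^4 = 0.185 (simulated 0.182 to 0.188). Reading one term named beforehand gives 0.05.

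The unstated choice thus moves the rate between 5% and 40%. Both layouts are balanced ANOVA approximations; the SAP selects its mixed model by fit, so neither figure describes that procedure exactly.

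**Step 4: the price of correcting**

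The documents give no HbO2 effect size, so starting power is assumed. With the same F test, noncentralities of 10.03, 5.16 and 2.89 give 80%, 50% and 30% power at 0.05. The Bonferroni level for ten tests is 0.05/10 = 0.005. The Benjamini-Hochberg columns come from simulation at correlations 0 and 0.5.

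| Power at 0.05 | Lone effect, at 0.005 | Lone effect, Benjamini-Hochberg | All ten effects true, Benjamini-Hochberg |
|---|---|---|---|
| 80% | 48.5% | 48–49% | 74–77% |
| 50% | 19.2% | 19–20% | 36–37% |
| 30% | 8.1% | 8–9% | 13–17% |

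Adding M1 and posterior parietal as outcomes would make 7 × 2 = 14 tests. The uncorrected rate becomes 1 − 0.95^14 = 0.512, and Benjamini-Hochberg power for a lone effect that started at 80% falls to about 45%.

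**The case for a change.** The strongest case for acting is that a region list, a channel map and a sentence on model structure cost little. M1 is the hardest gap to explain: it was chosen for the cap in a study of movement and then has no outcome. Broad objectives do not account for that, and only a map would separate relabelling from reselection. This stands as a remark on completeness. It does not show that any reported outcome would be wrong.

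It can also be said that the task question is not confined to fNIRS. The SAP compares the primary speed outcome in both ST and DT, under the same loosely specified models. Two separate tests at 5% give 1 − 0.95^2 = 0.0975 under independence. This too stands. It is softened because the closing paragraph of Protocol section 3 and the SAP's Brief summary both make dual-task performance the secondary aim, which gives a natural order for reading the two results.

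The available remedies have faults of their own. A single group-by-time term averaged over regions and tasks neither localises an effect, as objective 2 asks, nor isolates transfer to the dual task, as objective 3 asks. Naming it in advance would also have to be squared with selecting the model by fit. A correction for HbO2 alone leaves HHb without a family. Adding the two unmatched regions enlarges the very multiplicity complained of.

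**Conclusion.** No change follows. The label difference is exact, three of five, but it lies between a hardware description and an analysis list whose coverage may overlap. The documents do not show that a planned outcome cannot be measured or that an objective is abandoned. Assigning channels to regions is something the analysts must do in any case, and it can be reported with the results.

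The multiplicity gap is real and conditional. If ten HbO2 tests were run separately and read uncorrected, the chance of at least one false positive would be about 22% to 40% for assumed correlations from 0.7 down to 0. It would be 5% for one pre-named term in a joint model. Against this, a correction across regions would take a lone effect from an assumed 80% power to about 49%. HbO2 is ranked secondary and HHb tertiary, the SAP names one primary behavioural outcome, and post-hoc tests are already corrected. Leaving the regional tests uncorrected and reading a single positive region as exploratory is a fair choice. The conclusion rests on that cautious reading and on regional coverage that the documents neither confirm nor rule out.

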### **Tertiary outcomes:**

## 1. Clinical balance outcome

The MiniBEST will be administered to assess general balance. The scale consist of 4 subscales: 1) anticipatory postural control; 2) reactive postural control; 3) sensory orientation; 4) dynamic gait. Total score (range 0-28) will be compared between the two days (pre, retention) and between the two groups (training, control).

## 2. fNIRS-outcomes

Cortical deoxygenated hemoglobin (HHb) will be measured with functional Near-Infrared Spectroscopy (fNIRS) in the same regions as HbO2. HHb levels will be determined and compare between the three test moments (pre, post, retention) and between the two groups (training, control) during the Wasp Game ST and Wasp Game DT.

### **Main analysis:**

Primary, secondary and tertiary outcomes will be compared between training and control group and pre, post and retention test using linear mixed models. We will determine the best model based on standard fitting criteria. . We will consider cognitive and balance skills as possible covariates, depending on between group differences and determined by a blind review of the data. Post-hoc testing will be corrected for multiple testing by Bonferroni corrections.

Depending on data normality, Pearson and/or Spearman correlation analysis will be performed between neural and behavioral outcomes within groups and test moments. Bonferroni corrections for multiple testing will be applied when necessary.

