2.4 Duration experiments

One session of \pm 3.5 hours, including 25 min of training, and one session of \pm 1.5u. There will be a period of 24 hours between both sessions.

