Fig. 3B shows that the player is in the middle of an area infested by wasps. By moving the CoM (displayed by the red dot) towards a pre-defined 80% of the fLOS, a water stream will come on to hit the wasp. The number of wasps hit, weight-shifting accuracy, comprising the CoM traject and target deviation, and speed are used as outcomes. The WASP-ST involves hitting wasps in the ML direction by shifting weight. **Fig. 3C** illustrates the WASP-DT. Participants have to perform a serial subtraction task as the secondary task, whereby the red ball (representing the CoM) will change color from red to white and white to red within a random interval between 2-5 seconds. A starting number will appear on the screen for 1.5 sec at the beginning of each trial. Every time the ball changes its color, subtractions have to be made in threes. Subjects will indicate the correct number afterwards, so as not to disturb the fNIRS recording.

5.3.2 *Study specific procedures*

On day 1, subjects in the training group will receive the WASP-training, consisting of 10 blocks of 2.5 minutes. Training will be adjusted to the individual fLOS targeting at least 80%. Before and after training, weight shifting ability will be assessed using the WASP-tests with and without serial subtractions. We will measure cortical activity with fNIRS during weight-shifting following recent guidelines¹¹. We propose a block design distinguishing periods of quite stance from weight shifting. Participants will undergo two blocks offered in a fixed order: I) WASP-ST; II) WASP-DT. Each block has a duration of 4m40s, starting with 20s quiet stance, followed by 20s weight-shifting, alternating in seven trials. This block design allows for the 4s-7s delay in the hemodynamic peak response by having sufficiently long periods of task exposure. Subjects are not allowed to speak, so as not to disturb the fNIRS signal. In the DT-condition, subjects will be asked to focus on the primary and secondary tasks equally. Subjects in the control group will not receive any form of training. Retention tests will occur on day 2 (24 hr). Also, simultaneous fNIRS measurements will be carried out. fNIRS was found to have adequate test-retest reliability¹⁸. Cap placement will be marked to facilitate accurate placement on day 2.

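### Leaving the mixed model's covariance to unnamed fit criteria can give the acquisition and retention contrasts wrong standard errors, in a direction that depends on correlations the documents do not give

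*SAP*

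**What the plan says.** Under its main analysis heading the SAP states: "Primary, secondary and tertiary outcomes will be compared between training and control group and pre, post and retention test using linear mixed models". It then says "We will determine the best model based on standard fitting criteria". Covariates are handled in a separate sentence, and post-hoc tests are to be Bonferroni-corrected. Protocol 6.2 adds only the two factors: "A linear mixed model will analyze learning effects with training group as between-subject and pre-post-retention as within subject factor". Neither document names random effects, a covariance structure, the candidate models, a criterion, a degrees-of-freedom method or a fallback.

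The three moments are unevenly spaced. Protocol 5.3.2 puts pre and post on day 1 ("Before and after training, weight shifting ability will be assessed using the WASP-tests with and without serial subtractions") and retention on day 2. Protocol 2.4 gives the gap: "There will be a period of 24 hours between both sessions". Between pre and post, only one arm is trained: "On day 1, subjects in the training group will receive the WASP-training, consisting of 10 blocks of 2.5 minutes".

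**The concern.** The selection sentence does not mention covariance. But covariates have their own sentence, and in a mixed model the structure is one of the things that fit criteria are commonly used to choose, so the reading is fair.

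One plausible choice is a random intercept. It imposes a single correlation and a single residual variance on all three pairs, so pre-post, pre-retention and post-retention all get the same standard error. That is correct only if the three changes are equally variable. Two tests within a session and a third a day later give reason to doubt it, and so does training placed between the first two in one arm.

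The protocol's objectives separate acquisition from consolidation, so each contrast needs its own valid standard error. Under the stated rule, a fit statistic chosen after the data are seen would set it.

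**Working it through.** **Inputs.** From the documents: 20 per arm, alpha 0.05, 80% power, pre/post by group interaction, comparator 0.0916 (SD 0.0350) m/s and trained 0.1094 (SD 0.0418) m/s (Protocol 5.1). The within-person correlations are not given, so all values below are assumptions, listed as pre-post / pre-retention / post-retention.

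**The plan's own figure.** Pooled SD = sqrt((0.0350² + 0.0418²)/2) = 0.0386. d = 0.0178/0.0386 = 0.462 and f = d/2 = 0.231. With an assumed correlation of 0.5, lambda = f² × 40 × 2/(1 − 0.5) = 8.5 on 1 and 38 df, and power is 0.812. The stated 40 is reproduced, using two time points and one correlation, so it says nothing about the third moment. Whether f = d/2 suits an interaction is a separate question. The simulations below do not rely on it, because the effect was set to give 80% power with unstructured covariance.

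**Standard errors by arithmetic.** With unit variances, the variance of a change is 2(1 − correlation). At 0.8/0.6/0.6 the three changes have variances 0.4, 0.8 and 0.8. A common-correlation model uses their mean, (0.4 + 0.8 + 0.8)/3 = 0.667, for all three. Model SE over true SE is then sqrt(0.667/0.4) = 1.29 for pre-post and sqrt(0.667/0.8) = 0.91 for each retention contrast. At 0.6/0.6/0.8 the same sum gives 0.91, 0.91 and 1.29, so pre-post is now too narrow.

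**How often the criteria choose it.** Unstructured covariance has 6 parameters and common correlation has 2. For the 4 extra parameters AIC charges 8. BIC charges 4 ln 40 = 14.8 if n is participants, or 4 ln 120 = 19.1 if n is observations. Results of 20,000 simulated trials per pattern (20 per arm, complete data, REML):

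| Assumed correlations | SE ratio pre-post | pre-retention | post-retention | Common chosen, AIC | BIC, n = 40 |
|---|---|---|---|---|---|
| 0.6/0.6/0.6 | 1.00 | 1.00 | 1.00 | 90% (correct) | 99% (correct) |
| 0.7/0.5/0.5 | 1.20 | 0.93 | 0.93 | 56% | 90% |
| 0.8/0.7/0.7 | 1.15 | 0.94 | 0.94 | 69% | 95% |
| 0.8/0.6/0.6 | 1.29 | 0.91 | 0.91 | 35% | 77% |
| 0.9/0.7/0.7 | 1.53 | 0.88 | 0.88 | 5% | 30% |
| 0.6/0.6/0.8 | 0.91 | 0.91 | 1.29 | 35% | 77% |
| 0.8/0.64/0.8 | 1.13 | 0.84 | 1.13 | 28% | 71% |
| training 0.6/0.6/0.8, control 0.8/0.6/0.6 | 1.05 | 0.91 | 1.05 | 76% | 97% |

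At 0.8/0.6/0.6, BIC with n = 120 chooses the common structure in 91% of trials.

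**Consequences at 0.8/0.6/0.6**

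| | Unstructured | Common | AIC | BIC |
|---|---|---|---|---|
| Pre-post power | 80% | 62% | 76% | 68% (n = 40), 65% (n = 120) |
| Unadjusted type I error, retention contrasts | about 5% | about 7.4% | about 5.7% | 6.6–7.2% |
| Familywise error, three contrasts at 0.05/3 | 4.5% | 4.8% | 4.8% | 5.0% |

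At 0.6/0.6/0.8 it is pre-post that exceeds its level, with about 7% type I error under the common structure. Unstructured covariance held type I error between 4.6% and 5.3% for every contrast in every pattern.

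**The case against.** **Direction.** A reader might infer that acquisition errors will be too wide and retention errors too narrow. The documents do not support that. It requires pre-post to be the highest correlation, and no correlation is given. Training between pre and post may loosen that link in one arm; the acquisition ratio then shrinks to 1.05, and it reverses to 0.91 if post-retention is the highest in both arms. Pre-retention was too narrow in every unequal pattern tried, but the sign for the other two contrasts depends on the pattern.

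**Overall error rate.** It is also tempting to say that the trial's error rate is inflated. Under the planned Bonferroni correction it is not: the three-contrast family stays near 5%. What remains is that the error is unevenly shared, so single contrasts do not keep their stated level.

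**Size.** Under AIC the loss is about 4 points of power and under 1 point of type I error, and the largest misfits are mostly caught (at 0.9/0.7/0.7 AIC chooses the common structure in 5% of trials). The larger losses need BIC or a forced random intercept. The SAP names neither, but excludes neither.

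**Cap placement.** Protocol 5.3.2 says "Cap placement will be marked to facilitate accurate placement on day 2". Re-placing the cap bears on the fNIRS outcomes only. Weight-shifting speed comes from centre-of-mass data, so for the primary outcome only the timing argument applies.

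**Layout.** Three moments need only six covariance parameters if single task (ST) and dual task (DT) are modelled separately with one value per moment. A joint ST and DT model has six values per person and 21 parameters. The fix must therefore state the layout.

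**Conclusion.** The point holds in conditional form. The covariance and the criterion are not prespecified. If the three correlations differ moderately, common criteria at 40 participants often select a structure that gives the contrasts wrong standard errors. The size runs from small (AIC) to 12–15 points of pre-post power and about 2 points of unadjusted retention type I error (BIC, 0.8/0.6/0.6). It is nil if the correlations are equal. These figures rest on assumed correlations, normal and complete data, and 20 per arm.

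The direction cannot be stated from the documents, but the remedy does not depend on it. The change is worth making because it takes a data-driven choice out of the primary analysis at almost no cost. It does not put the design in doubt. It does not apply to the MiniBEST, which the SAP compares at two moments only.

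**What to change.** Limit the selection sentence so that it does not cover covariance, and add to the SAP's main analysis:

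> For each outcome measured at pre, post and retention, analysed separately for ST and DT with one value per test moment, the model uses an unstructured 3 x 3 within-participant covariance, REML and Kenward-Roger degrees of freedom; the covariance is not selected on fit. If the model does not converge, each group contrast is tested on its own change score.

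With complete data the change-score test is the same comparison on 38 df, so the fallback keeps each contrast's own standard error. Heterogeneous Toeplitz would be a poor fallback: it makes pre-post and post-retention share one correlation, and at 0.8/0.6/0.6 it gives SE ratios of 1.20 and 0.88 for those two contrasts.

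The cost is one SAP passage and a standard software option; the sample size stays at 40. If the correlations are in fact equal, power is 80% instead of 81%, because 38 df replace 76 (critical t 2.024 against 1.992; 2.024/1.992 = 1.016, so intervals are about 1.6% wider).
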